7.9.5.1. Missing Data Analyses

Source data verification will aid in the reduction of missing, or incomplete data in the DHR. Due to the non-interventional nature of this data collection, complete avoidance of missing or implausible data is impossible, however minimal missing data is expected as fields in the DHR will be mandatory or monitored to ensure completeness of the data for analysis. Therefore, data completeness will be evaluated and the proportion of missingness will be reported for inclusion and exclusion criteria, exposure variables, covariate variables, and outcome variables. Data missingness will be described and compared across Cohorts. Baseline characteristics in participants with and without missing data will be compared among participants with complete data versus those with any missing data. Missing data imputation will be considered based on the presence of patterns of missingness and effect of missing data on the interpretability of the results. If a covariate is included in the propensity score model and has more than 40% missingness, that covariate will be excluded from the propensity score model. However, among *a priori* selected covariates in the propensity score model with less than 40% missing data, multiple imputation applying the fully conditional specification method (FCS) will be used.⁶¹ The FCS method, also called chain equations method, imputes missing data in a dataset through an iterative series of predictive models. In each iteration, the specified variable is imputed

using other variables in the dataset. FCS is a flexible multiple imputation method and can handle various types of variables, such as binary, ordinary, or continuous variables.⁶² Categorical variables will be imputed using the discriminant function, continuous variables using ordinary linear regression, ordinal variables using ordinal logistic regression, and binary variables using logistic regression.

Missing data imputation will be conducted for missing month (to derive age) however, other data fields will not be imputed. An assumed day and month of birth (01 July) for all participants will be implemented to describe approximate age of participants at index.

7.9.6. Interim Analysis

Interim results will be reported at 18 months, 36 months, and 54 months after study initiation. Each interim analysis will include the following results:

At the 18-month interim analysis, the Roctavian and SoC Cohorts will be described, the propensity scores will be built and assessed for performance, and all outcome analyses will be descriptively reported. Among participants that have at least one year of follow-up, comparative analyses will be performed. The 18-month interim analysis will also evaluate the number of enrolled participants who withdraw consent from the study or are otherwise censored.

The 36- and 54-month interim analyses will include all comparative analysis results, although follow-up times will be variable among included participants.

Study sites will be asked to update data for all AbD participants approximately 6 months prior to each planned interim analysis and will be supported by site monitors through on-site monitoring and routine monitoring visits to ensure that all available data for enrolled participants are recorded into the DHR prior to the planned interim analysis.

7.9.6.1. Futility Analysis

A futility analysis will be conducted at the 18-month interim analysis to assess whether the study should be terminated early due to the inability to meet the required sample size for comparative analyses. Discontinuation criteria for the study will involve if either of the following conditions are met (unless there is an indication that recruitment is expected to considerably increase during the remainder of the recruitment period) at the 18-month interim analysis/report:

- Roctavian Cohort is expected to include ≤ 33 persons (<50% of the target sample size for the Roctavian Cohort)
- SoC Cohort is expected to include <67 persons (target sample size of the Roctavian Cohort)

Based on these discontinuation criteria, the futility analysis will examine the total number of participants enrolled in the study, the number of participants in each of the SoC and Roctavian Cohorts and the amount of time remaining in the study recruitment window. Assessments of potential futility and implications on study interpretation will be discussed in the reports associated with these interim analyses.

A futility assessment will also be included as part of the 36-month and 54-month interim analyses to determine the observed ABR of each Cohort. The sample size calculation conducted *a priori* (see section 7.6) will be re-calculated based on the observed ABR of each cohort at these timepoints. Implications on study interpretation will be discussed in the reports associated with these interim analyses.

Continued conduct of the study as described in the original study protocol based on the futility assessment at these timepoints will be discussed with the G-BA. Any changes to the conduct of the study and AbD based on the futility assessment will be made in agreement with the G-BA.

7.9.7. Implausible Data and Outliers

Given the data may be skewed, outliers will be checked by boxplot. IQR is defined as the difference between the 3rd and 1st quartile. Observations that are below ($Q1 - 1.5 \times IQR$) or above ($Q3 + 1.5 \times IQR$) will be evaluated (except for bleed counts which may have excess zeros). Also, individual data points that do not align with biologically or clinically plausible values (e.g., participant weight <10 kg, participant with >50 bleeds per year) will be reviewed and removed if determined to be implausible. For linear regression models, residual analysis will be conducted and Cook's distance will be computed to measure the influence of individual data points.⁶³

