10.3.2.3. Hypothetical Estimand

Analyses based on the hypothetical estimand will describe outcomes during the follow-up period for both the Roctavian Cohort and SoC Cohort, minimizing time periods during which outcomes are confounded by exposure to both gene therapy and SoC prophylaxis. As PwSHA administered Roctavian will remain on prophylaxis for a time following the index date as endogenous FVIII production initiates, the analytical follow-up period for outcomes such as bleeding events and hemostatic therapy utilization for the Roctavian Cohort will begin 5 weeks post-infusion or 3 days after the end of routine FVIII prophylaxis (whichever occurs later), or 27 weeks after end of emicizumab prophylaxis consistent with analyses of the Roctavian clinical trials. The analytical follow-up period of the SoC Cohort will begin on the index date. Participants in the Roctavian Cohort will be censored at the time of resumption of SoC prophylaxis and participants in the SoC Cohort who subsequently receive Roctavian during follow-up after the recruitment period, will be censored on the date of Roctavian infusion. As with the treatment policy estimand, for both cohorts a participant’s time in the analysis will be censored in the event of a withdrawal, loss to follow-up, death or

enrollment in an interventional trial. Follow-up will be censored based the earliest date after index of any of the censoring events described above.

Figure 3 below illustrates the hypothetical estimand analysis.

Figure 3: Analysis Schema for Hypothetical Estimand

[figure not shown]

Figure note: For the Roctavian Cohort, analytical follow-up period for outcomes such as bleeding events and hemostatic therapy utilization will begin on 5 weeks post-infusion or 3 days after the end of routine FVIII prophylaxis (whichever occurs later), or 27 weeks after end of emicizumab prophylaxis consistent with analyses of the Roctavian clinical trials. Participants in the Roctavian Cohort will be censored at the time of resumption of SoC prophylaxis. For the SoC Cohort, analytical follow-up period of the SoC Cohort will begin on the index date. Participants in the SoC Cohort who subsequently receive Roctavian during follow-up after the recruitment period, will be censored on the date of Roctavian infusion.

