10.3.6. Primary Objective

10.3.6.1. Objective: To compare the annualized bleeding rate for treated bleeds.

Annual bleeding rates for treated bleeding events (see [Table 6](#)) will be compared between the Roctavian Cohort and SoC Cohort after PS adjustment. *A priori* the PS adjustment is planned to be implemented via IPTW. All participants with the variables recorded to derive the PS will be included in the analysis. Participants with no bleeds reported but data entered into the DHR will have an ABR of zero (ie, data is not considered missing).

ABRs will be compared over the full follow-up time for each participant in the study, as well as during annual increments during the follow-up. For analyses of annual increments, only those participants who have full follow-up for the time will be included in analyses. For example, analyses comparing ABRs during the first year will only include participants with ≥ 1 year of follow-up after the index date or analyses comparing ABRs through 2 years of follow-up will only include participants with ≥ 2 year of follow-up after the index date.

Sample sizes are expected to be reduced in analyses of annual increments for interim analyses as data collection will be ongoing, and potentially reduced for final analyses due to censoring (see below).

ABRs will be calculated for each participant as the number of bleeds divided by the time between the start of follow-up and censoring event for the analysis, annualized to the number in 1 year. The mean of the individual participant ABRs for each cohort will be calculated and compared. The primary comparison of ABRs will be based on the absolute difference in the mean treated ABR between the Roctavian Cohort and SoC Cohort utilizing a two-sample t-test (two-sided).

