11.8. Study Monitoring

Selected sites will be managed and monitored throughout the duration of the study according to the approved Clinical Operations Plan (ie, study monitoring plan). Trained and qualified personnel from the sponsor or a designee will oversee site participation and data quality by means of both remote site management and on-site visits.

Prior to commencing activities, an on-site, site initiation visit will be performed at each study site selected to participate and will be performed by monitors trained to conduct site initiation visits. Training of the monitors will be performed by the sponsor or designee.

During the initiation visit, monitors will train physicians and appointed site personnel involved in this study, on the protocol, procedures and the creation and maintenance of accurate source records.

On-site monitoring visits will involve 100% source data verification on all data fields relating to inclusion and exclusion criteria and primary endpoint data fields against entries made into the DHR. A further 10% of randomly selected participants will have all remaining endpoints source data verified against entries made into the DHR.

All source data should be captured in source medical records that are standard practice for the site. Examples of source documents that may be used in this study may include: Participant medical notes and/or records; Site specific source document worksheets, if used; Laboratory reports and other test results; Informed Consent Forms; Hospital records for associated SAEs; Patient Reported Outcomes questionnaires.

Source data verification will aid in the reduction of missing, or incomplete data in the DHR, however due to the non-interventional nature of this routine data collection, complete avoidance of missing or implausible data is impossible.

To ensure timely completeness of data into the DHR, on-site and remote site visits will be performed, and it is anticipated that at least 2 routine on-site monitoring visits, per annum, per site will be conducted. The first on-site monitoring visit will be performed within 4 weeks of inclusion of the first participant at each study site.

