7.9.3. Analysis of Primary Outcome

Population	Measurement Period	Analysis Notes
All participants For interim and analyses at fixed timepoints, only those with specified amounts of follow-up will be included	≥1 year of follow-up, ≥2 years of follow-up, ≥3 years of follow-up, all available follow-up	Participants with no bleeds will be included as having an ABR of 0

The primary objective to compare the ABR for treated bleeds between the Roctavian and SoC Cohorts will be measured by annualizing the number of bleeds reported in the DHR. Follow-up for ABR will begin as of the index date for the SoC and Roctavian Cohorts. Bleeds will be identified if participants have an “occasion” for treatment of spontaneous bleeding/hemorrhage (regardless of severity). Participants may have multiple bleeds during the reporting period. To calculate ABR, a count of the number of bleeds for each participant will be divided by the number of days in the relevant time period for each participant, multiplied by 365.25. The mean of the individual ABRs for each Cohort will be calculated and then compared between Cohorts over the full follow-up time, as well as during annual increments during the follow-up. For analyses of annual increments, only those participants with full follow-up for that timepoint will be included. For example, analyses comparing ABRs during the first year will only include participants with ≥1 year of follow-up after the index date or analyses comparing ABRs through two years of follow-up will only include participants with ≥2 year of follow-up after the index date. Sample sizes are expected to be reduced in analyses of annual increments for interim analyses as data collection will be ongoing.

Mean, SD, median, IQR, minimum and maximum will be reported for the primary outcome by study group. Histograms will be plotted for the primary outcome by study group. SMD will be calculated to compare Roctavian and SoC Cohort. The participant number in the two Cohorts will be weighted using IPTW generated from the propensity score model. Both unadjusted and propensity score adjusted results will be reported and compared.

Given treated bleeds are event based, a IPTW weighted negative binomial model will be fit to compare ABR between Roctavian and SoC Cohort, with negative binomial distribution and log link function, and the log transformed follow-up time as the offset variable. IPTW will be applied to create

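### SAP 7.9.7 lets high bleed data be removed from the primary endpoint on judgement, with no masking to cohort, source-based criterion or with-and-without analysis specified

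*Protocol*

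**What the plan says.** SAP 7.9.7 sets up two checks. The boxplot check exempts bleeds ("except for bleed counts which may have excess zeros"). The second check covers "individual data points that do not align with biologically or clinically plausible values"; one of its two examples is a "participant with >50 bleeds per year) will be reviewed and removed if determined to be implausible". The section does not say who reviews, whether they see the cohort, or what makes a value implausible beyond the examples. Nor does it say whether the threshold is an observed count or an annualised rate, or plan an analysis that keeps the removed values.

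Three other places determine what the check can do:

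- **ABR.** SAP 7.9.3 takes each participant's bleed count "divided by the number of days in the relevant time period for each participant, multiplied by 365.25". Results are reported for at least 1, 2 and 3 years of follow-up and for all available follow-up; the last has no minimum. Protocol 10.3.6 adds that "The mean of the individual participant ABRs for each cohort will be calculated and compared".
- **Window.** SAP 7.9.3 states that "Follow-up for ABR will begin as of the index date for the SoC and Roctavian Cohorts". Under the hypothetical estimand (Protocol 10.3.2.3, SAP 7.2.3) the Roctavian window opens only after prophylaxis has ended, and "Participants in the Roctavian Cohort will be censored at the time of resumption of SoC prophylaxis".
- **Verification.** Protocol 11.8 plans "100% source data verification on all data fields relating to inclusion and exclusion criteria and primary endpoint data fields".

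**The concern.** Removal is triggered by the size of the outcome and settled by judgement after the data are seen. Nothing written prevents the reviewer from knowing the cohort, and no second analysis would show what the removal did to the estimate. In a cohort of about 67 a single high value carries weight, so one discretionary decision can move the result.

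The threshold adds a further problem. Dividing by a short observation time turns a small, real count into a large annualised rate. Under the hypothetical estimand a Roctavian participant who bleeds soon after stopping prophylaxis and then resumes it has such a short window. Follow-up in the SoC Cohort has no matching end that bleeding brings about.

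**Working it through.** **Inputs.** From SAP 7.6 (also Protocol 10.1): ABR 3 for SoC and 0.85 for Roctavian, dispersion 1.5, exposure 1 year, allocation ratio 0.2, margin 0.5, one-sided 2.5%, power 80%, 330 + 67 = 397 participants. From SAP 7.9.3: ABR = bleeds ÷ days × 365.25. From SAP 7.9.7: threshold 50 per year.

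**1. The plan's own figure.** With the SAP 7.6 formulas:

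- V1 = 1/3 + 1/(0.2 × 0.85) + 1.2 × 1.5/0.2 = 15.22
- V0 = 1.1²/(0.5 × 0.2 × 3.17) + 9 = 12.82
- N1 = (1.960√12.82 + 0.842√15.22)² ÷ (ln 0.5 − ln 0.2833)² = 328.8, so 329
- N2 = 0.2 × 328.8 = 65.8, so 66

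The total is 395 against 397 stated. The inputs reproduce the plan's figure closely enough to use below.

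**2. Bleeds needed to exceed 50 per year if the flag is annualised.** This is the smallest k with k × 365.25/d > 50.

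| Days observed | 7 | 14 | 21 | 28 | 90 | 180 | 365 | 1,095 |
|---|---|---|---|---|---|---|---|---|
| Bleeds | 1 | 2 | 3 | 4 | 13 | 25 | 50 | 150 |

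For example, 1 × 365.25/7 = 52.2.

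**3. How often full follow-up trips it.** With the planned negative binomial (mean 3, dispersion 1.5, 1 year), P(more than 50) = 0.0000123 per SoC man, so 330 × 0.0000123 = 0.004 expected. For 67 Roctavian men it is essentially 0. The flag therefore matters almost only for short windows or truly extreme bleeders.

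**4. How often a short window trips it.** The documents give no bleeding rate off prophylaxis. Assuming Poisson bleeding at 10 to 40 per year, the chance of a flag is 17–54% in 7 days, 6–45% in 14, 1–37% in 28 and 0–20% in 90. It is at most 7% over 1 year and 0.4% over 3 years.

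**5. Effect of one removal on the mean of individual ABRs.** One man at 52.2 among 67, the other 66 at 0.85: (66 × 0.85 + 52.2)/67 = 1.62 kept, 0.85 removed.

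**6. Effect of one removal in the offset negative binomial model.** Unweighted simulation at the planned rates, 330 + 67 men, 300 runs per scenario (288 to 300 usable). The criterion is an upper 95% limit below 0.5; removal drops the participant.

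| One Roctavian man | Others followed | Median rate ratio, kept vs removed | Criterion met, kept vs removed |
|---|---|---|---|
| 3 bleeds in 21 days | 1 year | 0.31 vs 0.28 | 61% vs 83% |
| 3 bleeds in 21 days | 3 years | 0.30 vs 0.28 | 78% vs 92% |
| 51 per year, full follow-up | 1 year | 0.52 vs 0.28 | 0% vs 81% |
| 51 per year, full follow-up | 3 years | 0.53 vs 0.28 | 0% vs 89% |

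The Monte Carlo standard error of the 61% is √(0.61 × 0.39/288), about 3 percentage points.

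**The case against.** The strongest reply is that this is an ordinary data-entry check. It stands beside a body-weight example, concerns single data points, and removes nothing until someone has reviewed it. Bleed counts are spared the boxplot rule. Edit checks and manual checks (Protocol 11.5, SAP 7.7) and full source verification make a true count recognisable. Protocol 10.5 also promises to quantify data excluded as implausible. All of this stands, and it makes a wrongful removal less likely. But quantifying exclusions does not show their effect on the estimate, and SAP 7.9.7 does not tie the decision to verification.

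The short-window route is also narrow. It needs the annualised reading, which is plausible because the SAP defines ABR per year, but which the text does not fix. Return to prophylaxis means a physician-reported return to continuous use; on-demand treatment or short-term prophylaxis would not close the window. Bleeds at the same site within 3 days of the last treatment are merged (SAP Table 5). Under treatment policy, follow-up starts at index and runs on after prophylaxis resumes. These points make the 7-day case extreme without excluding windows of a few weeks.

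Finally, the 0.5 criterion is the SAP's (7.9.3). Protocol 10.1 says the actual null hypotheses are not shifted, and a rate ratio of 0.31 is still far from 1. That limits what a short-window removal could change to the SAP's shifted test and to the size of the estimated effect.

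A reader might infer that analysts who know the cohort will delete true Roctavian failures. The documents do not support that. Absence of masking is not a statement that review is unmasked, and removal requires a judgement of implausibility. Nor is the direction fixed: the same check could remove high SoC bleeders, for instance men treated on demand for part of baseline (Protocol 10.5, SAP 7.10), which would work against Roctavian.

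**Conclusion.** The point holds as a gap in SAP 7.9.7. Primary-endpoint data can be removed because they are high, in either cohort, without specified masking, a source-based criterion or an analysis that keeps them.

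One removal is material. It moves the Roctavian mean of individual ABRs from 1.62 to 0.85, and changes the chance of meeting the 0.5 criterion by about 22 percentage points (83 − 61) or 14 (92 − 78) in the short-window case. A truly extreme bleeder with full follow-up would decide that test outright.

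These sizes rest on the planned rates and dispersion, an unweighted model and exactly one affected man. The short-window case also assumes an annualised flag, and is confined to the hypothetical-estimand, all-available-follow-up analysis or to otherwise very short follow-up. It does not reach treatment policy at full follow-up, where 150 bleeds in 3 years would be needed, or the analyses requiring at least 1 year.

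A reader might also want to know how often this would happen. That depends on the early-failure rate and the bleeding rate off prophylaxis, which the documents do not give, so no frequency is claimed. This is a low-cost improvement to the SAP; it is not evidence that results will be biased.

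**What to change.** Amend SAP 7.9.7 as follows:

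- Apply the bleed plausibility flag to observed counts, not to annualised rates.
- Review flagged bleed records masked to cohort.
- Correct errors against source, and keep every source-verified bleed whatever its size.
- If a value cannot be verified, report the primary analysis with and without it, and list such values by cohort.

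The cost is SAP wording and one masked listing. No new data are needed, because source verification of the primary-endpoint fields is already planned. The downside is that genuine extreme values stay in and may widen the confidence interval.

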7.10. Limitations of the Statistical Analysis

This study has several limitations inherent to the observational nature of the study and use of registry data.

- **Selection bias:** Selection bias is a distortion of evidence or data that arises from the way that the data are collected. Participants eligible for, and who consent to participate in, this study may not be representative of the overall population of PwSHA in Germany, limiting the generalizability of findings from that data.
- **Confounding bias:** Confounding bias occurs when the effects of a treatment or the exposition effect of the disease vary by the presence/level of another factor (effect modifier). Due to the absence of participant randomization, Roctavian and SoC therapies may be prescribed to groups of participants with prognostic differences, thus limiting generalizability of results. The analytic approach of using propensity scores aims to account for these differences. The study team will exercise flexibility in the propensity score weighting scheme to ensure optimal balance between the exposed and unexposed populations indexed. However, unobserved/unmeasured confounding may still be present. To account for possible unmeasured confounding, a quantitative bias assessment will be performed.
 - In addition to variables that are not feasible to capture in an observational registry, the non-interventional nature of the study reflecting a range of real-world practice in Germany could introduce confounding that cannot be fully addressed with PS or specific applications of the PS (e.g. matching). For example, PwSHA are recommended to be treated with hemostatic prophylaxis, though a small portion of the severe hemophilia A population in Germany may still be utilizing an on-demand treatment regimen. Persons utilizing an on-demand regimen are likely to have a higher baseline bleeding rate, as prophylaxis is associated with reduced bleeding events. All persons administered commercially available Roctavian are expected to have received hemostatic prophylaxis treatment for at least 12 months by the time that a participant will be treated with Roctavian gene therapy. If persons treated with an on-demand regimen for part of the baseline period enroll into the SOC Cohort, these participants may have outlier propensity scores which may not be able to be matched. The proportion of on-demand participants in the SOC Cohort, as well as impact of these participants on the analysis will be discussed in interim and final reports.
- **Loss to follow-up:** Participant retention through the end of the expected observation period will be monitored carefully and attempts will be made to obtain follow-up data from participants who discontinue treatment. However, some participants may have fewer than three years of follow-up data available. Participants in the SoC Cohort are expected to have follow-up twice per year whereas participants in the Roctavian Cohort may have more frequent touchpoints due to them being on a newer treatment.
- **Missing data:** The data leveraged for this study are dependent on physicians and hospitals to accurately record each event. Methods are in place for handling missing data (Section 9.7.5) and a sensitivity analysis of missing data will be conducted.
- **Heterogeneity of SoC:** The assumption of treatment consistency specifies that there is no ambiguity defining a treatment. This assumption is also known by the term "treatment variation irrelevance". For this study, the two compared treatment groups are Roctavian versus SoC with SoC being different for various participants. Therefore, treatment consistency is approximately

met if these different SoC treatments are considered to result in approximately equal treatment effects. As outlined in Section 7.4.2, SoC prophylaxis treatment types were assumed to have similar efficacy, QoL, and safety profiles, and therefore, are pooled together as one SoC control Cohort. While there is minimal evidence that prophylactic SoC treatments are largely heterogeneous regarding efficacy, QoL and safety profiles, a sensitivity analysis will be performed to analyze the SoC treatment types separately, as outlined in Section 7.9.5, and results may be reported for each SoC treatment separately if necessary.

- **Measurement error:** Measurement error is the difference between a measured quantity and its true value. Data in the DHR are collected for more general purposes (not specifically for this study), therefore, some medical information not directly related to this study may be incomplete or not available at all. The consistency of the available information may vary across study years since the data are entered by physicians based on general patient follow-up. This can affect the measurement of exposure to SoC treatments, the outcomes of interest and/or the covariates. To ensure that the accuracy of the retrieved information is acceptable, all data will be reviewed for possible inconsistencies or implausible information.

